# **5.1.10. Visit 9**: **Phone visit** (Nine weeks after initiating study drug)

During this follow-up visit study:

- Patient will be reminded to:
  - stop study drug from second bottle
  - remove ZIO-Patch
  - return the medication bottle, diary and ZIO-Patch in a pre-paid mailer to the University of Rochester.
- Adverse events will be assessed and reported.

## **5.1.11. Visit 10: Phone visit** (Ten weeks after initiating study drug)

During this follow-up visit:

- An ICD interrogation (with a manual transmission by patient, if system is not automatic) from remote device monitoring system will be obtained.
- Adverse events will be assessed and reported.
- Subject will be informed by study personnel regarding subsequent medical management regarding antiarrhythmic medications to be taken after the closeout of the study as per decision of enrolling center physician.
- Close out the study participation of the subject.

## 5.2. Treatment Dosage and Administration

Each subject will take 1 blinded capsule of study drug (flecainide or a placebo) dose BID per randomization scheme for 28 days. After 28 days there will be a 7-day washout period. At the end of the washout period, each subject will then take 1 blinded capsule of study drug (flecainide or placebo) for the next 28 days.

## 5.3. Efficacy Assessments

During this pilot clinical trial, efficacy of flecainide on cardiac rhythm will be assessed by 7-day ECG monitoring with ZIO-Patch to determine overall burden of premature ventricular contractions. In addition, remote ICD monitoring of the subjects previously implanted ICD device will be used to account for episodes of ventricular tachycardia ventricular fibrillation.

## 5.4. Safety Assessments

The assessments that will be performed to evaluate safety include medical history, standard 12-lead ECG, implanted device interrogation and the use of the 7-day ZIO-Patch monitor and will be quantified by:

a) VPBs on 7-day ECG monitoring to determine the possibility of proarrhythmia defined as a 3-fold increase in number of VPBs;

b) Total burden of nun-sustained and sustained (ICD treated and untreated) VT episodes on interrogation of ICDs evaluated after the first week and after the fourth week of study drug administration with a 5-fold increase in number of VT episodes defining proarrhythmia.

c) QRS prolongation on ECG defined as >40ms in comparison to baseline and the new presence of the Brugada pattern of the ECG. We expect 17-29% prolongation of the QRS but prolongation >30% (40ms) will be unusual. The appearance of cove-type Brugada pattern will be monitored.

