# **1.2.** Purpose of the Study

The primary specific aim of this pilot trial is to determine whether flecainide administration is associated with a significant reduction in the number of ventricular premature beats (VPBs) in ARVC patients with ICDs.

The secondary aims are to:

- 1) Assess safety of flecainide administration with particular emphasis on pro-arrhythmic response measured by:
  - a. VPBs on ECG monitoring
  - b. Nonsustained and sustained VT/VF episodes documented on ICD interrogation
  - c. Effects of flecainide on QRS morphology and duration.
- 2) Assess the effects of flecainide on the number of VT runs in 7-day ECG recordings.
- 3) Assess the effects of flecainide on the frequency of atrial premature beats in 7-day ECG recordings.
- 4) To demonstrate feasibility of enrollment of rare arrhythmia ARVC patients in a randomized study in preparation for the planned future large clinical trial with VT/VF as the primary endpoint.

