# 5.1.4. Visit 3: Phone visit (One week after initiating study drug)

During this follow-up visit:

• An ICD interrogation (with a manual transmission by patient, if system is not automatic) from remote device monitoring system should be obtained.

- Study drug prescribing regimen, diary and importance of compliance will be reviewed with subject.
- Adverse events will be assessed and reported.
- **5.1.5. Visit 4**: **In person visit in home or in clinic** (Three weeks after initiating study drug) During this follow-up visit:
  - A standard 12-lead ECG recording will be performed.
  - Blood sample will be drawn for flecainide levels. A teaspoon (5ml) of blood is needed for this sample. This blood sample will be sent to a specialized lab. Paper copy of ECG will be uploaded to the Box.com at the University of Rochester.
  - A ZIO-Patch (a small, adhesive, water-resistant one lead ECG recorder) will be applied to the chest for a continuous 24-hour monitoring over 7 days. ZIO-Patch could be self-applied or applied by study staff member. At the end of the 7 days the patch must be removed and returned to the University of Rochester
  - Review study drug prescribing regimen, diary and importance of compliance will be reviewed with subject.
  - Adverse events will be assessed and reported.

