# **5.1.8. Visit 7**: **Phone visit** (Six weeks after initiating study drug)

During this follow-up visit:

- An ICD interrogation (with a manual transmission by patient, if system is not automatic) from remote device monitoring system will be obtained.
- Study drug prescribing regimen, diary and importance of compliance will be reviewed with subject.
- Adverse events will be assessed and reported.
- **5.1.9. Visit 8**: In person visit in home or in clinic home visit (Eight weeks after initiating study drug)

During this follow-up visit:

- A standard 12-lead ECG recording will be performed.
- Blood sample will be drawn for flecainide levels. A teaspoon (5ml) of blood is needed for

this sample. This sample will be sent to a specialized lab for analysis and paper copy of ECG will be sent to the University of Rochester.

- A ZIO-Patch (a small, adhesive, water-resistant one lead ECG recorder) will be applied to the chest for a continuous 24-hour monitoring over 7 days. ZIO-Patch could be selfapplied or applied by study staff member. At the end of the 7 days the patch must be removed and returned to the University of Rochester
- Study drug prescribing regimen, diary and importance of compliance will be reviewed with subject.
- Adverse events will be assessed and reported.

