# 11. RISK/BENEFIT ASSESSMENT

# 11.1. Potential Risks

## 11.1.1. Potential Risks to Patients Undergoing Treatment with Flecainide

Flecainide is an antiarrhythmic drug approved by the Food and Drug Administration in the US since 1982 to suppress cardiac arrhythmias and is predominantly used for atrial arrhythmias. Flecainide was studied in the CAST trial (Echt et al. 1991) in patients after myocardial infarction with ventricular arrhythmias and was associated with a higher incidence of mortality or non-fatal cardiac arrest (19/323) as compared with its matching placebo (7/318). The most serious adverse reactions reported for flecainide in patients with ventricular arrhythmias were new or exacerbated ventricular arrhythmias which occurred in 6.8% of patients and new or worsened congestive heart failure which occurred in 3.9% of patients. In some patients, flecainide treatment has been associated with episodes of unresuscitatable ventricular tachycardia or ventricular fibrillation. There have also been instances of second- (0.5%) or third-degree (0.4%) AV block. A total of 1.2% of patients developed sinus bradycardia, sinus pause, or sinus arrest. The frequency of most of these serious adverse reactions probably increases with higher trough plasma levels, especially when these trough levels exceed 1.0  $\mu$ g/mL, unlikely to occur with our propose dose of 100 mg bid.

Patients with structural heart disease, treated with flecainide for supraventricular arrhythmias, may be at increased risk for proarrhythmia and cardiac adverse events. The use of

flecainide in these patients has been associated with life-threatening and occasionally fatal ventricular arrhythmias. Therefore, in these patients, especially in the presence of impaired left ventricular function with ejection fraction  $\leq 40\%$ , flecainide should be used with extreme caution, preferably after other antiarrhythmic drugs have been tried or considered inappropriate. Because flecainide has a mild negative inotropic effect, it may cause or worsen congestive heart failure, particularly in patients with cardiomyopathy, pre-existing severe heart failure (NYHA functional class III or IV) or ejection fractions  $\leq 40\%$ . Flecainide should therefore be used cautiously in patients who are known to have a history of congestive heart failure or myocardial dysfunction. When used per current FDA approved prescription information flecainide is considered a safe drug.

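### Section 5.4(b) defines ICD proarrhythmia without VF, a comparator, a rate or a zero-count rule, dilutes sustained VT, and uses timing that conflicts with the interrogation schedule

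*Combined protocol and SAP*

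**What the plan says.** Secondary aim 1 in Section 1.2 is safety, with emphasis on proarrhythmic response. Item b of that aim lists "Nonsustained and sustained VT/VF episodes documented on ICD interrogation" as one of its measures. Section 5.3 likewise says that remote ICD monitoring "will be used to account for episodes of ventricular tachycardia ventricular fibrillation".

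Section 5.4(b) puts the measure into operation. The threshold is worded "with a 5-fold increase in number of VT episodes defining proarrhythmia". The device data are to be "evaluated after the first week and after the fourth week of study drug administration". The quantity counted is given as "Total burden of nun-sustained and sustained (ICD treated and untreated) VT episodes on interrogation of ICDs". The section names no reference period, no time denominator and no rule for a reference of zero. By contrast, item (c) of the same section refers QRS change to baseline.

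Section 14.3 repeats the timing for the DSMB: interrogations after 1 and 4 weeks of each treatment. Table 2 ticks remote ICD interrogation only at Visits 3, 7 and 10. The visit text places these at week 1, at week 6 (Visit 7 is headed "Six weeks after initiating study drug") and at week 10. None is scheduled before the drug starts, and none at Visit 5, the end of the first 28-day period.

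**The concern.** A proarrhythmia definition should pick up the events it exists to find and stay quiet when nothing has changed. Read as written, this one has trouble on both counts.

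- VF does not enter the count, so the rule does not cover the aim it serves.
- Brief runs and shocked VT carry equal weight, so frequent runs set the denominator and a few serious episodes barely move the ratio.
- A subject with no reference episodes has no ratio. Yet Section 11.1.1 warns of "new or exacerbated ventricular arrhythmias which occurred in 6.8% of patients", and a new arrhythmia is one that may start from zero.
- A raw count depends on how long the device was counting, and the scheduled intervals differ in length.

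The pilot is meant to inform a larger trial with VT/VF as primary endpoint. A proarrhythmia frequency that omits some serious events and may include artefacts would be a poor basis for judging whether that trial is safe to run.

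**Working it through.** **The plan's own figures.** The plan gives no false-alarm rate or other operating characteristic for this rule, so there is none to reproduce. Its power table for the primary endpoint does reproduce (0.836, 0.624, 0.988 and 0.903 against 84%, 62%, 99% and 90%), but it does not bear on this point.

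**Dilution.** With b reference episodes and nonsustained VT unchanged, reaching 5b needs 4b added episodes. For b = 1, 5, 10 and 20 that is 4, 20, 40 and 80 added sustained episodes. Ten runs followed by 10 runs plus 3 treated VTs gives 13/10 = 1.3-fold. One added episode gives 11/10 = 1.1-fold.

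**Zero reference.** Zero episodes followed by 4 treated VTs gives 4/0, which is undefined. At an assumed Poisson rate of 0.5 per week, a 4-week reference has mean 2, and P(0) = exp(−2) = 13.5% of subjects. Section 14.2 plans similar methods for secondary outcomes as for log2(VPB); a log transform of a zero count is also undefined.

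**Windows implied by the schedule.** The first bottle covers days 0–28, washout days 28–35, and the second bottle days 35–63.

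- To Visit 3: days 0–7, 7 days, all first bottle.
- Visit 3 to Visit 7: days 7–42, 35 days = 21 first bottle + 7 washout + 7 second bottle.
- Visit 7 to Visit 10: days 42–70, 28 days = 21 second bottle + 7 after it stops.

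At a constant rate the expected Visit 7/Visit 3 ratio of counts since the last interrogation is 35/7 = 5, the threshold itself. With the ±2-day visit windows it runs from 31/9 = 3.4 to 39/5 = 7.8.

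**Chance of meeting the threshold with no change in rate.** Let X and Y be independent counts in the reference and later windows. The probability is P(X ≥ 1 and Y ≥ 5X), over all subjects. The documents give no episode rate or dispersion, so both are assumptions.

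| Rate per week | 1 v 5 weeks (Visit 3 v Visit 3–7), Poisson | Week 1 v weeks 2–4 (Section 5.4 timing), Poisson | 4 v 4 weeks, Poisson | 4 v 4 weeks, negative binomial k = 1 |
|---|---|---|---|---|
| 0.5 | 3.3% | 0.6% | 1.4% | 3.2% |
| 1 | 21.2% | 6.8% | 2.8% | 7.1% |
| 2 | 42.5% | 21.6% | 0.6% | 10.8% |

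At 5 to 20 per week the 1 v 5 week figure is 52–53%. The matched Poisson figure stays at or below about 3% over 0.5 to 20 per week. If episodes cluster strongly (negative binomial, k = 1), the matched figure rises to 16% at 20 per week.

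**The case against.** Four points can fairly be made for the plan.

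First, sustained VT is explicitly in the count. A reader might infer that the rule cannot register new sustained VT at all. That is not so: a rise from 1 to 5 sustained episodes qualifies. Nor do the documents say that a zero-reference subject can never qualify; they are silent.

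Second, nothing says that the first-week count is to be set against the whole Visit 3–7 interval, which belongs to no single treatment. On the Section 5.4 timing the window ratio is 3, not 5, and the chance figures are lower. In a crossover, flecainide against placebo is at least as natural a reading: the VPB rule in 5.4(a) has no pre-drug 7-day recording to refer to either. So 21.2% or 42.5% must not be read as the trial's false-alarm rate. The corresponding 33% and 49% among subjects with at least one first-week episode are not shares of all subjects.

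Third, a reader might infer that the trial would miss a VF or a treated VT altogether. It would not. Aim 1b measures VT/VF, Section 10.2 documents tachyarrhythmias from interrogations, Section 14.2 tabulates adverse events by treatment, and Section 14.3 sends ICD-treated arrhythmias and deaths to the DSMB.

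Fourth, if transmitted episodes carry time stamps, unequal intervals need not distort anything.

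All four stand as limits on the point. None supplies the missing comparator, rate, zero rule or VF term, and none resolves the timing conflict. Case review by the DSMB does not change the definition used to classify subjects.

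**Conclusion.** The concern holds for the definition, not for safety capture as a whole. Four parts follow from the text alone: VF is omitted against aim 1b, pooling dilutes sustained VT, no comparator, rate or zero rule is given, and weeks 1 and 4 of treatment conflict with interrogations at weeks 1, 6 and 10.

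The size of the unequal-window effect is conditional. It needs a raw comparison of counts since the last interrogation, which the plan neither states nor rules out, and it rests on assumed rates and Poisson variation. Matching windows removes the built-in bias, but not all chance firing if episodes cluster. The definition should be corrected before proarrhythmia is classified; the primary analysis is unaffected.

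**What to change.** 1. Add VF to Section 5.4(b). Report VF and sustained or ICD-treated VT as a component separate from nonsustained VT, by treatment period, whatever the fold change.
2. Use device time stamps to assign each episode to flecainide, placebo or washout time. Compare episodes per day over matched windows with the placebo period as comparator. State a rule for zero counts, for example a separate category for subjects with none on placebo and some on flecainide, alongside the difference in daily rate, which is defined at zero. Applying the rule with the periods swapped would show how often it fires by chance.
3. Reconcile the week 1/week 4 timing in Sections 5.4(b) and 14.3 with Table 2 and the visit text.

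A fixed 28-day pre-drug reference is not advisable. Section 5.1.1 requires a washout of at least 5 days, so such a window could include time on an antiarrhythmic, and a rise could then reflect its withdrawal.

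The cost is protocol wording and a little more data handling, assuming transmitted episode lists are dated. Some older episodes may be missing from device memory, and subjects with only one period have no matched comparator and would be described separately. This alters endpoint classification only, not clinical management.

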# 3.2. Inclusion and Exclusion Criteria

Inclusion criteria:

- Age > 18 years.
- Subjects who have been diagnosed with ARVC and meet 2010 Modified Task Force Criteria for ARVC as affected.
- At minimum 500 VPBs on the most recent 24-hour Holter monitor recording prior to consent or after consent if a subsequent recording is required after 5 day washout following discontinuation of anti-arrhythmic medication.
- Functioning implanted cardioverter defibrillator with remote interrogation capability.
- Subjects should be on a beta-blocker including metoprolol, propranolol, atenolol, nadolol, carvedilol or bisoprolol unless contraindication to beta-blockers exists.
- Persons prescribed quinidine, procainamide, propafenone, disopyramide, dronedarone phenytoin, mexilitene, may be included after 5 day washout period with subsequent 24-hour Holter obtained after washout period.
- Persons prescribed sotalol may be included after 5 day washout period during which another beta-blocker may be administered with subsequent 24-hour Holter obtained.
- Subject and personal physician and or cardiologist must agree not to use any antiarrhythmic medications during the 10 weeks of participation, unless needed for management of life-threatening arrhythmias.
- All subjects must agree to use medically acceptable contraceptive measures during participation unless documented as surgically sterile or post-menopausal (no menstrual periods for more than one year).

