#### Table 2. Schedule of Activities.

	Visit	Visit	Visit 2	Visit	Visit	Visit	Visit	Visit	Visit	Visit	Visit
	0 a Screen	1 a Ran- domize	Drug Initia- tion	3	4	5	6 Second Drug Bottle	7	8	9	10 Close- out
Start Medication Weeks	-4-0 weeks	-4-0 weeks	0	1 week + 2 days	3 weeks + 2 days	4 weeks + 2 days	5 weeks + 2 days	6 weeks + 2 days	8 weeks + 2 days	9 weeks + 2 days	10 weeks + 2 days
In person visit	Yes in clinic	No	No By phone	No by phone	In home or in clinic d	No by phone	No by phone	No by phone	In home or in clinic d	No by phone	No by phone
Study Periods			Period	1			Period 2	2			
Informed Consent	√										
Pregnancy Test b	√										
Medical History	√										
Holter Monitor c	✓										
ECG	✓				✓				✓		
Randomization		✓									
Blood Sample					√				✓		
7-day ECG Monitor					√				✓		
Remote ICD interrogation				√				✓			✓
Adverse event				✓	√	✓	√	✓	✓	√	✓
Drug Dispense/Accountability			~				~			~	
Stop and return study drug and ZIO-Patch						~				~	
Study Closeout											✓

a - Visits 0 and 1 could be done on the same day.

b - Pregnancy test must be obtained prior to randomization

c – Holter Monitor for subjects have had a washout of antiarrhythmic therapy

d - Visit at home will be done by specialized services with: ECG recording and blood draw; ZIO-Patch could be self-applied by

subject or by study staff member. These visits could take place in a clinic if this is what subject and investigator are agreeable to.

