# 5.1. Visits

## 5.1.1. Visit 0: Subject Screening and Consent

Each potential subject will have inclusion and exclusion criteria verified by study personnel prior to approaching a potential subject for consent. The consent process begins with the protocol described to them by one of the physicians or research coordinators at the enrolling site. Potential subjects will sit down with the coordinator or physician and have the opportunity to ask questions. Those who meet inclusion/exclusion criteria will then be asked to sign consent for study participation. At this time they will sign an "informed consent" form that is fully approved by the local IRB following local IRB consent administration regulations. It is the responsibility of the investigator to ensure that subjects are eligible to participate in the study prior to enrollment and throughout the study. Once informed consent has been obtained, all screening tests and procedures have been assessed and study eligibility has been confirmed, subjects will be assigned a unique subject identification number. The enrolling site will enter data in the web base system and the system will assign the subject ID after study eligibility criteria are met. The scheme for assigning subject ID is as follow: first 2 numbers are assigned for enrolling site and will not change for duration of the study. Next two numbers are specific to a randomized subject in the enrolling site.

The principal investigator ensures that informed consent from each potential research participant will be obtained by an IRB approved consent designee and documented. The following persons may obtain consent: the principal investigator, sub-investigators, or study team members listed on the IRB application form as a consent designee. Each individual who will interact with potential research participants to obtain consent will submit evidence of human subject compliance training per local IRB regulations.

After written informed consent is obtained, a medical history and an ECG will be obtained from the subject. Any woman of childbearing age must have a negative pregnancy urine or blood test prior randomization, unless the woman is surgically sterile or post-menopausal (no menstrual periods for more than one year). Investigators will verify that subjects must use a medically acceptable method of birth control prior to study entry and while participating in the study.

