Subjects are expected to be on one of the following beta-blockers unless contraindicated: metoprolol, propranolol, atenolol, nadolol, carvedilol or bisoprolol. Subjects on antiarrhythmic medications including: sotalol, mexilitene, flecainide, quinidine, procainamide, propafenone, disopyramide, dronedarone, or phenytoin will require washout lasting a minimum of 5 days and a subsequent 24-hour Holter recording demonstrating at least 500 VPBs prior to being considered for randomization. Study sites are provided with dedicated Holter recorders to be used if needed. Patients should return Holter recorders in person or by mail to the enrolling site personnel who will upload Holter files into the University of Rochester Box.com system for analysis. Enrolling centers will be informed about the results of 24-hour Holter analysis within 2 business days. Subjects not meeting eligibility criteria of at least 500 VPBs in 24-hour Holter after washout of medication used prior to the study drug initiation will be withdrawn and replaced.

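### The QRS and Brugada flags are read against a baseline ECG that need not follow washout, so they can under-count in subjects coming off a prior antiarrhythmic

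*Combined protocol and SAP*

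**What the plan says.** Section 5.4(c) flags "QRS prolongation on ECG defined as >40ms in comparison to baseline" together with "the new presence of the Brugada pattern of the ECG". It does not say which recording is the baseline.

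Table 2 (Schedule of Activities) has ECGs at Visits 0, 4 and 8 only, so Visit 0 supplies the only one before study drug. Section 5.1.1 fixes its timing by consent alone: "After written informed consent is obtained, a medical history and an ECG will be obtained from the subject".

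Washout can come after consent. Section 3.2 lets the qualifying Holter be recorded "after consent if a subsequent recording is required after 5 day washout following discontinuation of anti-arrhythmic medication". Section 5.1.1 says that subjects on sotalol, mexiletine, "flecainide, quinidine, procainamide, propafenone, disopyramide, dronedarone, or phenytoin will require washout lasting a minimum of 5 days", and then "a subsequent 24-hour Holter recording demonstrating at least 500 VPBs prior to being considered for randomization". The only washout footnote in Table 2 sits on the Holter row: "Holter Monitor for subjects have had a washout of antiarrhythmic therapy". The recheck at Visit 1 (Section 5.1.2) concerns the VPB count on the Holter. No section asks for an ECG after washout.

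**The concern.** A change-from-baseline flag works only if the baseline is free of the effect being looked for. Where the Visit 0 ECG was taken on a drug that widens the QRS, part of any later widening is already in the reference and is subtracted away. The same holds for the Brugada pattern: if a prior drug had already brought it out, its appearance on flecainide would not count as new.

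The error runs in one direction, towards too few flags. Safety is the first secondary aim in Section 1.2, and QRS morphology and duration are named in it. If the order of ECG and washout is not recorded, the analyst cannot later tell which baselines are affected, and no other pre-treatment ECG is scheduled to replace them.

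**Working it through.** **1. Can the protocol be followed exactly and still give an on-drug baseline?** Yes. Visit 0 is the only in-person visit before study drug. Visit 1 needs no contact with a subject who is still eligible (Section 5.1.2), Visit 2 is by phone (Section 5.1.3), and the Holter may come back by mail (Section 5.1.1). A subject can consent, have the ECG, stop the prior drug, wear the Holter and be randomised without a second ECG.

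**2. Formula.** Let Q be the drug-free QRS, w the fraction by which the prior drug widens it, and D the true rise on study drug over Q.

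- Recorded baseline: Q(1 + w)
- On-treatment value: Q + D
- The flag fires when Q + D − Q(1 + w) > 40, that is, when **D > 40 + wQ**

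**3. The plan's own figures.** Section 5.4 equates 40 ms with 30%, which implies Q = 40/0.30 = 133 ms. At that Q the expected 17–29% prolongation is 22.7–38.7 ms, just below the flag. With a drug-free baseline (w = 0) the flag fires above 40 ms, as intended.

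**4. With an on-drug baseline.** The 5–10% range for w and the Q values of 100 and 120 ms are assumptions. The 17–29% is the plan's expectation for flecainide, and 133 ms is the value implied in step 3.

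| Q (ms) | w | True rise needed (ms) |
|---|---|---|
| 100 | 5% | 40 + 5 = 45 |
| 100 | 10% | 40 + 10 = 50 |
| 120 | 5% | 40 + 6 = 46 |
| 120 | 10% | 40 + 12 = 52 |
| 133 | 17% | 40 + 22.7 = 62.7 |
| 133 | 29% | 40 + 38.7 = 78.7 |

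The last two rows apply only if the prior drug was flecainide and its residual effect equals what the plan expects of the study dose. A true rise of 60 ms at Q = 133 ms would then read as 60 − 38.7 = 21 ms to 60 − 22.7 = 37 ms and would not be flagged.

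**5. Drug lists.** Section 5.1.1 names flecainide among the drugs needing washout. The washout criteria in Section 3.2 and the disallowed list in Section 6 do not name it. Whether the flecainide rows can arise depends on which list governs.

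**6. Secondary point: ICD readings.** Sections 5.4(b) and 14.3 put the readings after 1 and 4 weeks of each treatment. Table 2 schedules study weeks 1, 6 and 10. Period 1 runs over weeks 0–4 and period 2 over weeks 5–9.

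- Week 1 is one week into period 1, and week 6 is 6 − 5 = 1 week into period 2. Both match.
- No reading falls at week 4, the end of period 1. The next is at week 6, after the washout week and the first week of period 2.
- The last is at week 10, which is 10 − 9 = 1 week after period 2 ends.

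Only the four-week readings are mismatched.

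**The case against.** The best reply is that Table 2 puts the ECG and the post-washout Holter in the same Visit 0 column, with a window of −4 to 0 weeks, and that its footnote speaks of subjects who have already had a washout. A site can take the ECG after washout, and many may. That stands: the gap is a missing requirement, not a rule that makes the baseline wrong.

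It is also fair that the consequence is limited. The QRS aim is answered mainly by comparing the Visit 4 and Visit 8 ECGs under the model in Section 14.2, and that comparison uses no baseline ECG. No stopping or withdrawal rule hangs on the 40 ms flag, and the main-focus list for the DSMB in Section 14.3 does not name the 12-lead QRS. A subject is affected only if washout was needed, the ECG came first, the prior drug widened the QRS, and the true rise lies between 40 ms and the raised threshold. The documents give a QRS effect for flecainide alone.

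Four stronger readings are tempting but not supported:

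- *The flag fires late.* There is one scheduled ECG per treatment period, so it fires or it does not.
- *The 40 ms and 30% figures contradict each other.* They agree at 133 ms, and the documents give no QRS distribution against which to test that.
- *The 3-fold VPB flag has the same fault.* Section 5.4(a) rests it on the 7-day recording, which is made only on treatment. It names no comparator, but the Visit 0 ECG does not enter it.
- *The Brugada pattern will be missed altogether.* Section 5.4(c) also says its appearance will be monitored; what can be too low is the count of new cases.

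**Conclusion.** The point holds, and the plan should be changed. In subjects whose Visit 0 ECG preceded washout of a QRS-widening drug, the effective threshold rises from 40 ms to 40 + wQ ms: 45–52 ms under the assumed 5–10% and 100–120 ms, and about 63–79 ms at 133 ms if the prior drug was flecainide. The QRS count, and the count of new Brugada patterns, can be too low in these subjects. How many there will be cannot be derived from the documents, so no number of missed flags can be given.

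The result assumes that the prior drug is still acting at the Visit 0 ECG and that washout of at least five days would have removed its effect. The primary VPB analysis and the continuous flecainide-minus-placebo QRS contrast are untouched. A reader might infer that the trial's QRS findings as a whole are biased. They are not; the problem is confined to the individual flags.

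**What to change.** 1. State in Sections 5.1.1 and 5.4 and in Table 2 that the baseline ECG for the QRS and Brugada flags is recorded after completed washout and before the first dose, within the existing Visit 0 window and alongside the post-washout Holter. Record in the case report form whether it came before or after the end of washout.
2. Where it came before, mark the subject and use the placebo-period ECG (Visit 4 or 8, already collected) as the reference in the final count.
3. Report the flags by treatment period. Add a sensitivity count that uses the placebo reference for every subject, so that one table does not mix two definitions. Under the placebo reference only the flecainide period can be flagged, so state the denominators.
4. Reconcile the ICD reading times in Sections 5.4(b) and 14.3 with Table 2, and state how VT episodes are assigned to period 1, washout, period 2 and the week after it.
5. Reconcile the drug lists in Sections 3.2, 5.1.1 and 6.

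**Cost.** Wording and one recorded item, with no new type of test. A subject who consents before washout may have to attend again within the window; step 2 covers those who cannot. The placebo reference is not available for real-time DSMB review, nor for subjects who stop before the placebo period. Such subjects keep only the marked baseline and may still be under-flagged.
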